### **Non-serious Adverse Event Collection and Reporting**

#### **Laboratory Test Abnormalities**

All laboratory test results captured as part of the study should be recorded following institutional procedures. Test results that constitute SAEs should be documented and reported to BMS as such.

The following laboratory abnormalities should be documented and reported appropriately:

- any laboratory test result that is clinically significant or meets the definition of an SAE
- any laboratory abnormality that required the participant to have study drug discontinued or interrupted
- any laboratory abnormality that required the subject to receive specific corrective therapy.

It is expected that wherever possible, the clinical rather than laboratory term would be used by the reporting investigator (eg, anemia versus low hemoglobin value).

**10. Other Safety Considerations.** Any significant worsening noted during interim or final physical examinations, electrocardiograms, X-rays, and any other potential safety assessments, whether or not these procedures are required by the protocol, should also be recorded as a non-serious or serious AE, as appropriate, and reported accordingly.

## 8.2 Recording of Adverse Events

At each contact with the subject, the study team must seek information on adverse events by specific questioning. Information on all adverse events should be recorded immediately in the source document, and also in the appropriate adverse event section of the case report form (CRF). All clearly related signs, symptoms, and abnormal diagnostic, laboratory or procedure results should be recorded in the source document.

All adverse events occurring during the study period must be recorded. The clinical course of each event should be followed until resolution, stabilization, or until it has been ultimately determined that the study treatment or participation is not the probable cause. Serious adverse events that are still ongoing at the end of the study period must be followed up, to determine the final outcome. Any serious adverse event that occurs after the study period and is considered to be at least possibly related to the study treatment or study participation should be recorded and reported immediately.

## 8.3 Reporting of Serious Adverse Events and Unanticipated Problems

When an adverse event has been identified, the study team will take appropriate action necessary to protect the study participant and then complete the Study Adverse Event Worksheet and log. The sponsor-investigator will evaluate the event and determine the necessary follow-up and reporting required.

### 8.3.1 Sponsor-Investigator reporting: notifying the Mayo IRB

The sponsor-investigator will report to the Mayo IRB any UPIRTSOs and Non-UPIRTSOs according to the Mayo IRB Policy and Procedures. Any serious adverse event (SAE) which the Principal Investigator has determined to be a UPIRTSO will be reported to the Mayo IRB as soon as possible but no later than 5 working days after the investigator first learns of the problem/event.

Information collected on the adverse event worksheet (*and entered in the research database*):

- Subject's name:
- Medical record number:

- Disease/histology (if applicable):
- The date the adverse event occurred:
- Description of the adverse event:
- Relationship of the adverse event to the research (drug, procedure, or intervention):
- If the adverse event was expected:
- The severity of the adverse event: (use a table to define severity scale 1-5)
- If any intervention was necessary:
- Resolution: (was the incident resolved spontaneously, or after discontinuing treatment)
- Date of Resolution:

The sponsor-investigator will review all adverse event reports to determine if specific reports need to be made to the IRB and FDA. The sponsor-investigator will sign and date the adverse event report when it is reviewed. For this protocol, only directly related SAEs/UPIRTSOs will be reported to the IRB.

### **8.3.2 Sponsor-Investigator reporting: Notifying the FDA**

The sponsor-investigator will report to the FDA all unexpected, serious suspected adverse reactions according to the required timelines, formats and requirements.

Unexpected fatal or life threatening suspected adverse reactions where there is evidence to suggest a causal relationship between the study drug/placebo and the adverse event, will be reported as a serious suspected adverse reaction. This will be reported to the FDA on FDA Form 3500A, no later than 5 business days after the sponsor-investigator's initial receipt of the information about the event.

Other unexpected serious suspected adverse reactions where there is evidence to suggest a causal relationship between the study drug/placebo and the adverse event, will be reported as a serious suspected adverse reaction. This will be reported to the FDA on FDA Form 3500A, no later than 15 business days after the sponsor-investigator's initial receipt of the information about the event.

Any clinically important increase in the rate of serious suspected adverse reactions over those listed in the protocol or product insert will be reported as a serious suspected adverse reaction. This will be reported to the FDA on FDA Form 3500A no later than 15 business days after the sponsor-investigator's initial receipt of the information about the event.

Findings from other studies in human or animals that suggest a significant risk in humans exposed to the drug will be reported. This will be reported to the FDA on FDA Form 3500A, no later than 15 business days after the sponsor-investigator's initial receipt of the information about the event.

## **8.4 Medical Monitoring**

The Principal Investigators will oversee the safety of the study. This safety monitoring will include careful assessment and appropriate reporting of adverse events as noted above, as well as the construction and implementation of a site data and

safety-monitoring plan (see section 10 “Study Monitoring, Auditing, and Inspecting”). Medical monitoring will include a regular assessment of the number and type of serious adverse events.

## **9 Data Handling and Record Keeping**

### **9.1 Confidentiality**

Information about study subjects will be kept confidential and managed according to the requirements of the Health Insurance Portability and Accountability Act of 1996 (HIPAA). Those regulations require a signed subject authorization informing the subject of the following:

- What protected health information (PHI) will be collected from subjects in this study
- Who will have access to that information and why
- Who will use or disclose that information
- The rights of a research subject to revoke their authorization for use of their PHI.

In the event that a subject revokes authorization to collect or use PHI, the investigator, by regulation, retains the ability to use all information collected prior to the revocation of subject authorization. For subjects that have revoked authorization to collect or use PHI, attempts should be made to obtain permission to collect at least vital status (long term survival status that the subject is alive) at the end of their scheduled study period.

### **9.2 Source Documents**

Source data is all information, original records of clinical findings, observations, or other activities in a clinical trial necessary for the reconstruction and evaluation of the trial. Source data are contained in source documents. Examples of these original documents, and data records include: hospital records, clinical and office charts, laboratory notes, memoranda, subjects' diaries or evaluation checklists, pharmacy dispensing records, recorded data from automated instruments, copies or transcriptions certified after verification as being accurate and complete, microfiches, photographic negatives, microfilm or magnetic media, x-rays, subject files, and records kept at the pharmacy, at the laboratories, and at medico-technical departments involved in the clinical trial.

### **9.3 Case Report Forms**

The study case report form (CRF) is the primary data collection instrument for the study. All data requested on the CRF must be recorded. All missing data must be explained. If a space on the CRF is left blank because the procedure was not done or the question was not asked, write “N/D”. If the item is not applicable to the individual case, write “N/A”. All entries should be printed legibly in black ink. If any entry error has been made, to correct such an error, draw a single straight line through the incorrect entry and enter the correct data above it. All such changes must be initialed and dated. Do not erase or use “white-out” for errors. For clarification of illegible or uncertain entries, print the clarification above the item, then initial and date it. If the reason for the correction is not clear or needs additional explanation, neatly include the details to justify the correction.

## **Data Management**

A RedCap database system (DMS) for the collection, storage and management of all study data will be developed at Mayo Clinic Rochester. The RedCap database will provide for data entry (including data entry at the trial sites using a web portal and immediate storage of the data in the central database), data security, and reporting. The data management team will develop a data validation plan, rule set specifications, and programming logic to implement data validation rules. The rule set will include checks for missing fields, range checks, skip pattern-logic, and inter and intra form checks.

### **9.4 Records Retention**

The sponsor-investigator will maintain records and essential documents related to the conduct of the study. These will include subject case histories and regulatory documents.

The sponsor-investigator will retain the specified records and reports for;

1. Up to 2 years after shipment and delivery of the drug for investigational use is discontinued and the FDA has been so notified. OR
2. As outlined in the Mayo Clinic Research Policy Manual –“Access to and Retention of Research Data Policy”

Whichever is longer.

## **10 Study Monitoring, Auditing, and Inspecting**

### **10.1 Study Monitoring Plan**

This study will be internally monitored on a routine basis during the conduct of the trial. Clinical trial monitoring requires review of the study data generated throughout the duration of the study to ensure the validity and integrity of the data along with the protection of human research subjects. This will assist sponsor-investigators in complying with Food and Drug Administration regulations.

The investigator will allocate adequate time for such monitoring activities. The Investigator will also ensure that the monitor or other compliance or quality assurance reviewer is given access to all the study-related documents and study related facilities (e.g. pharmacy, diagnostic laboratory, etc.), and has adequate space to conduct the monitoring visit.

### **10.2 Auditing and Inspecting**

The investigator will permit study-related monitoring, audits, and inspections by the IRB, the sponsor, and government regulatory agencies, of all study related documents (e.g. source documents, regulatory documents, data collection instruments,

study data etc.). The investigator will ensure the capability for inspections of applicable study-related facilities (e.g. pharmacy, diagnostic laboratory, etc.).

Participation as an investigator in this study implies acceptance of potential inspection by government regulatory authorities and applicable compliance offices.

## **11 Ethical Considerations**

This study is to be conducted according to United States government regulations and Institutional research policies and procedures. This protocol and any amendments will be submitted to a properly constituted local Institutional Review Board (IRB), in agreement with local legal prescriptions, for formal approval of the study. The decision of the IRB concerning the conduct of the study will be made in writing to the sponsor-investigator before commencement of this study.

All subjects for this study will be provided a consent form describing this study and providing sufficient information for subjects to make an informed decision about their participation in this study. This consent form will be submitted with the protocol for review and approval by the IRB for the study. The formal consent of a subject, using the Approved IRB consent form, must be obtained before that subject undergoes any study procedure. The consent form must be signed by the subject and the individual obtaining the informed consent.

## **12 Study Finances**

### **12.1 Funding Source**

The (BMS/Pfizer American Thrombosis Investigator Initiated Research Program (ARISTA-USA) is established to fund innovative medical research from investigators in the United States. This study is funded through the competitive request for application (RFA) through this Bristol Myers Squibb/Pfizer Alliance funding program.

## **13 Publication Plan**

The success of this trial will depend largely on the number and quality of its scientific publications and presentations. The purpose of the policy established is to encourage and facilitate the presentation of trial analyses while providing guidelines that ensure appropriate use of the data, timely completion of manuscripts and presentations, equitable access to authorship, and adherence to established principles of authorship using the ICMJE criteria.

## Appendix A. Telephone Script:

**Protocol Title:** A Phase IV, Randomized, Double Blind Study Evaluating the Safety and Efficacy of Apixaban in Subjects with Calf Vein Thrombosis

**Principal Investigator:** [name]

Completed By: \_\_\_\_\_

Date: \_\_\_\_\_

Circle One: Day 7      Day 14      Day 30      Day 60      Day 90

"Good morning/afternoon. This is \_\_\_\_\_ calling from Mayo Clinic Rochester/Eau Claire/La Cross. May I speak to \_\_\_\_\_?" **(If participant is there proceed to the following)**

"I would like to ask you a few questions regarding your blood thinner medication, you are taking for the clinical trial in which you have been enrolled. This will allow us to gather very important information about the safety and benefit of using this medication in treating and preventing blood clots."

I would like to ask these questions related to our study after confirming your name:

---

1. Since your last visit, have you missed any doses of your blood thinner medication?  
\_\_\_\_ Yes,  
If yes, approximately how many doses do you estimate that you have missed? \_\_\_\_  
\_\_\_\_ No, I have not missed any doses of medication
2. Since your last visit, have you had another blood clot problem?  
\_\_\_\_ Yes, a DVT  
\_\_\_\_ Yes, a PE  
\_\_\_\_ Both a DVT and a PE  
\_\_\_\_ Yes, something else (e.g. an arterial clot)  
\_\_\_\_ No, I have not had any more clots.
3. While you have been taking this medication as recommended, have you experienced any major bleeding which required hospitalization or blood transfusion?  
\_\_\_\_ Yes  
If yes, please describe: \_\_\_\_\_  
\_\_\_\_ No
4. While you have been taking this medication as recommended, have you experienced any bleeding other than from injury?  
\_\_\_\_ Yes,  
If yes, please describe \_\_\_\_\_  
\_\_\_\_ No

5. Which of the following best applies to your current activity rating:

- A.  Fully active, able to carry on all pre-disease performance without restriction.
- B.  Restricted in physically strenuous activity, but able to walk and to carry out work of a light or sedentary nature (for example, light house work, or office work).
- C.  Able to walk and capable of all self-care but unable to carry out any work activities. Up and about more than 50% of waking hours.
- D.  Capable of only limited self-care, confined to bed or chair more than 50% of waking hours.
- E.  Completely disabled. Cannot carry on any self-care. Totally confined to bed or chair.

6. Have you started any new medications?

Yes

If yes, please list: \_\_\_\_\_

No

7. Have you had any new leg swelling?

Yes,

If yes, suggest that the patient see their medical provider

No

8. Have you had any new chest pain or shortness of breath?

Yes,

If yes, suggest that the patient see their medical provider

No

9. On a scale of 0 – 10, what is your current pain level for the involved leg with the blood clot?  
(circle one)

0      1      2      3      4      5      6      7      8      9      10

Do you have any questions for me?

Thank you for participating in our study.

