## **2 Study Objectives**

**Primary Objective:** There are two primary objectives. First, the primary efficacy outcome is to evaluate whether a strategy of active anticoagulation with apixaban is more effective than serial ultrasound imaging in the management of patients with isolated calf vein thrombosis (cDVT) for the prevention of the composite outcome including thrombus propagation, pulmonary embolism, recurrent venous thromboembolic events, and all-cause mortality.

Second, the principal safety outcome is to assess the combination of major and clinically relevant non-major bleeding for subjects randomized to apixaban vs. placebo control.

**Secondary Objective:** There will be two secondary objectives.

The first is to assess the timing of thrombus propagation. The current understanding of thrombus propagation is that if it occurs, it will occur within the first 2 weeks of

diagnosis. This concept of timing of thrombus propagation is the basis for current guideline endorsed approach which limits the requirement for repeated ultrasound up to 2 weeks only. Yet, this guideline recommendation has not been validated. Our study is poised to verify this assumption.

The second is to determine net clinical benefit or harm for the two strategies. The outcome of net clinical benefit or harm will be assessed as the composite of the primary efficacy outcome or the principal safety outcome up to day 90.

[figure not shown]

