#### **4.4.3 Data Collection and Follow-up for Withdrawn Subjects**

For subjects withdrawn from the study, follow-up data will be collected throughout the protocol defined follow-up period. This is regardless of compliance or tolerance with study medication, provided participants are willing to provide follow up examinations. This data is important to the integrity of the final study analysis since early withdrawal could be related to the safety profile of apixaban. If a subject withdraws consent to participate in the study, for subject safety reasons, attempts will be made to obtain permission to collect follow up information, whenever possible.

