## 7.2 Statistical Methods

### 7.2.1 Primary Hypothesis:

We hypothesize that apixaban 5 mg twice daily is associated with a significantly lower rate of the primary composite efficacy outcome compared to matched placebo in patients with calf DVT.

**7.2.1.2 Primary Efficacy Analysis:** All patients randomized to receive at least one dose of apixaban 5 mg or matching placebo control will be included in the primary analysis under intention to treat (see analysis sets below). The analysis of the primary composite endpoint will only include events occurring during the 3 months of study medication use.

Frequency of the primary composite efficacy endpoint will be tabulated by treatment arm without regard to the time the event was observed within the 3 month study period. The Cochran-Mantel-Haenszel test will be used to compare the event rates by treatment group. The pooled estimate of the odds ratio will be used as the primary measure of association for the study.

An exploratory analysis will investigate the time to event is defined as the time from randomization to the first occurrence of a primary composite efficacy outcome event. Patients who were lost to follow-up or who withdrew consent before the end of the three month treatment period will be censored at the last day the patient had a complete assessment for study outcomes within the 3 month study period. The incidence curves of VTE events will be plotted using the Kaplan-Meier estimator by treatment group. The difference in the incidences of the primary composite outcome at 3 months between treatment arms will be estimated and tested using a normal approximation of the binomial distribution.

**7.2.1.3 Safety Analysis:** All patients who received at least one dose of study medication will be included in the safety analysis. The analysis of major bleeding and clinically relevant non-major bleeding events will include those events which occurred during the 3 month study period. Major bleeding events observed later will be described separately.

Frequency of major bleeding and clinically relevant non-major bleeding will be tabulated by treatment arm. The incidence of major bleeding and clinically relevant non-major bleeding will be summarized as a combined endpoint and separate endpoints by treatment arm. The difference in the incidences of the combined endpoint at 3 months between treatment arms will be estimated and tested using a normal approximation of the binomial distribution.

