## 8 Safety and Adverse Events

### 8.1 Definitions

**1. Adverse Events.** An Adverse Event (AE) is defined as any new untoward medical occurrence or worsening of a preexisting medical condition in a clinical investigation participant administered study drug and that does not necessarily have a causal relationship with this treatment. An AE can therefore be any unfavorable and unintended sign (such as an abnormal laboratory finding), symptom, or disease temporally associated with the use of investigational product, whether or not considered related to the investigational product. The causal relationship to study drug is determined by a physician and should be used to assess all adverse events (AE). The causal relationship can be one of the following:

**Related:** There is a reasonable causal relationship between study drug administration and the AE.

**Not related:** There is not a reasonable causal relationship between study drug administration and the AE.

The term "reasonable causal relationship" means there is evidence to suggest a causal relationship.

Adverse events can be spontaneously reported or elicited during open-ended questioning, examination, or evaluation of a subject. (In order to prevent reporting bias, subjects should not be questioned regarding the specific occurrence of one or more AEs.)

**2. Serious Adverse Events.** Serious Adverse Event (SAE) is any untoward medical occurrence; results in death; is life-threatening (defined as an event in which the participant was at risk of death at the time of the event; it does not refer to an event which hypothetically might have caused death if it were more severe); requires inpatient hospitalization; or causes prolongation of existing hospitalization (see NOTE below); results in persistent or significant disability/incapacity; is a congenital

anomaly/birth defect; is an important medical event (defined as a medical event(s) that may not be immediately life-threatening or result in death or hospitalization but, based upon appropriate medical and scientific judgment, may jeopardize the subject or may require intervention [eg, medical, surgical] to prevent one of the other serious outcomes listed in the definition above.) (Examples of such events include, but are not limited to, intensive treatment in an emergency room or at home for allergic bronchospasm; blood dyscrasias or convulsions that do not result in hospitalization).

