### Pain assessment

On a scale of 0 – 10, what is your current pain level for the involved leg with the blood clot? (circle one)

0 1 2 3 4 5 6 7 8 9 10

Has patient had a documented recurrent venous thrombosis confirmed by imaging? (check one)

1  Yes 2  No

If yes: Date diagnosed: (mm/dd/yyyy) \_\_\_\_/\_\_\_\_/\_\_\_\_

Pulmonary Embolism (check one) 1  Yes 2  No

Lower extremity deep vein thrombosis (check one) 1  Yes 2  No

Upper extremity deep vein thrombosis (check one) 1  Yes 2  No  
(jugular, innominate, subclavian, axillary, brachial)

Splanchnic vein thrombosis (check one) 1  Yes 2  No  
(hepatic, portal, splenic, mesenteric, renal, gonadal)

Cerebral vein thrombosis 1  Yes 2  No

Fatal PE: (check one) 1  Yes 2  No

Was the VTE recurrence: (check one) 1  Symptomatic 2  Incidental

How was the thrombus confirmed?

1  Ultrasound 2  CT 3  MRI 4  VQ scan 5  Surgery 6  Autopsy

Arterial clot: (check one) 1  Yes 2  No

If Yes, (check all that apply)  MI  
 TIA/Stroke  
 Peripheral embolism

Has patient had a major bleed? (check one) 1  Yes 2  No

If Yes, date of major bleed: (mm/dd/yyyy) \_\_\_\_/\_\_\_\_/\_\_\_\_-\_\_\_\_

If Yes (check all that apply)  Intracranial (intracerebral (hemorrhagic stroke), subarachnoid, subdural)

Intraspinal/epidural

Intraocular

Intraarticular

Intramuscular with compartment syndrome

Retroperitoneal

Pericardial

Fatal bleeding

GI

GU

Pulmonary

Other Specify: \_\_\_\_\_

Has patient had a clinically relevant non-major bleed? (check one) 1  Yes 2  No

If Yes, date of clinically relevant non-major bleed: (mm/dd/yyyy) \_\_\_\_/\_\_\_\_/\_\_\_\_-\_\_\_\_

If Yes, what were the consequences (check all that apply)

Required medical intervention

Unscheduled contact with health care team

Temporary cessation of study treatment

Has patient had a minor bleed? (check one) 1  Yes 2  No

If Yes, date of minor bleed: (mm/dd/yyyy) \_\_\_\_/\_\_\_\_/\_\_\_\_-\_\_\_\_

Last Date (any modality of) protocol therapy was given: (mm/dd/yyyy) \_\_\_\_/\_\_\_\_/\_\_\_\_-\_\_\_\_  
(date of last treatment dose on this study or date decision made to stop protocol treatment)

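### The day 30 and day 60 telephone questions on bleeding are narrower than the bleeding outcome they feed, so capture may be incomplete and may differ by arm

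*Combined protocol and SAP*

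**What the plan says.** Section 2 names bleeding as the second of two primary objectives: "the principal safety outcome is to assess the combination of major and clinically relevant non-major bleeding for subjects randomized to apixaban vs. placebo control". Section 7.2.1.3 sets the window, "The analysis of major bleeding and clinically relevant non-major bleeding events will include those events which occurred during the 3 month study period", and the population, "All patients who received at least one dose of study medication will be included in the safety analysis". Section 7.3 words the safety population more widely, as all randomized subjects; neither version has an adherence condition. For withdrawn subjects, Section 4.4.3 keeps data collection going to the end of the planned follow-up: "This is regardless of compliance or tolerance with study medication". The definitions in Section 3.3 turn on severity, site and consequence. None of them mentions the cause of the bleed or whether drug was being taken.

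The telephone script in Appendix A has two bleeding items. Item 3 asks about major bleeding that led to admission or transfusion. Item 4 is the general question: "While you have been taking this medication as recommended, have you experienced any bleeding other than from injury". Both open with the same condition on adherent use. Item 2, on clots, simply asks about the time since the last visit. The schedule in Section 6.2 places the telephone survey at days 30 and 60.

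On adverse events, Section 8.1 says that "subjects should not be questioned regarding the specific occurrence of one or more AEs", while Section 8.2 says that at each contact "the study team must seek information on adverse events by specific questioning".

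The follow-up case report form (Appendix B2) asks without conditions whether a major or a clinically relevant non-major bleed has occurred. Its consequence boxes for non-major bleeds are medical intervention, "Unscheduled contact with health care team" and temporary interruption of study drug.

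**The concern.** The analysis asks how many dosed patients bled in 3 months. The scripted questions ask how many bled while taking drug properly and, in the general question, without an injury. A patient who takes the wording literally can truthfully answer no to both items after a bleed that meets Section 3.3. Efficacy is asked about without conditions and safety with them, and the protocol gives no reason for the difference.

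At stake is the second primary outcome and, through it, the bleeding part of the net clinical benefit composite. Bleeding is likely to be infrequent in 250 patients, so even a few missed events matter. The patients most likely to fall outside the wording are those who stopped study drug, and stopping after a clot is expected more often on placebo.

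**Working it through.** **1. Endpoint and questions side by side.**

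| Feature | Analysis (3.3, 4.4.3, 7.2.1.3) | Item 3 | Item 4 | Item 2 (clots) |
|---|---|---|---|---|
| Time covered | whole 3 months | adherent use only | adherent use only | since last visit |
| Cause | any | any | injury excluded | any |
| Severity | major, or non-major meeting 3.3 | admission or transfusion | any | any |

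Two groups of bleeds fall outside both items 3 and 4: any bleed while off drug or not adherent, and an injury bleed that needed care but neither admission nor transfusion. The second kind can meet the medical-intervention or evaluation criterion in 3.3.

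**2. How much follow-up depends on the calls.** Visits are at days 7, 14 and 90, so 90 − 14 = 76 days contain no visit. The calls at days 30 and 60 are the only scheduled contacts in that stretch.

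**3. Why the gap may be unequal.** Section 4.4.1 has study drug stopped and another anticoagulant started after a confirmed clot. The plan gives no rate, power or sample size for bleeding; its only planning figure is for efficacy. With p1 = 0.10, p2 = 0.016, mean 0.058, two-sided alpha 0.0492 (z = 1.967) and 80% power (z = 0.842):

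n = [1.967·√(2 × 0.058 × 0.942) + 0.842·√(0.10 × 0.90 + 0.016 × 0.984)]² / 0.084² = 121 per arm, as stated.

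At 125 per arm the same rates give:
- Placebo: 125 × 0.10 = 12.5 patients with a clot.
- Apixaban: 125 × 0.016 = 2.0 patients with a clot.

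Later bleeds in these patients count in the analysis but lie outside items 3 and 4. For scale only, assume that 4% to 10% of them bleed. The lower value is the bleeding proportion that Section 1.1 reports for the heparin arm of the largest calf-vein trial; the upper value is an assumption. That gives 12.5 × 0.04 = 0.5 to 12.5 × 0.10 = 1.25 placebo patients, and 2.0 × 0.04 = 0.08 to 2.0 × 0.10 = 0.20 apixaban patients. At those rates these are ceilings, because they credit each patient with full follow-up, whereas a clot found at the day 90 scan leaves none.

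**4. Direction.** If a fraction c of bleeds is captured in both arms, the observed risk difference is c times the true one, which flatters apixaban on the absolute scale and leaves the risk ratio unchanged. If the loss is mainly of placebo bleeds after a clot, the observed difference grows, which counts against apixaban. The two effects have opposite signs, and the documents give no capture fraction with which to net them.

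**5. How little loss the comparison can bear (illustration, all rates assumed).** Power at 125 per arm, two-sided 0.05, is Φ{[d − 1.96·√(2p̄q̄/n)] / √[(p1q1 + p2q2)/n]}. This normal approximation is rough at such counts.

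| True rates, apixaban vs placebo | Expected events | Full capture | 80% | 60% |
|---|---|---|---|---|
| 4% vs 1% | 5.0 vs 1.25 | 33% | 27% | 21% |
| 10% vs 3% | 12.5 vs 3.75 | 61% | 51% | 40% |

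This shows sensitivity to incomplete capture. It does not estimate what the script loses.

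**6. Case report form against 3.3.** The non-major boxes have none for admission or a higher level of care, add drug interruption (not a criterion), and replace evaluation with unscheduled contact. The major-bleed list covers sites and fatal bleeding but has no field for hemoglobin fall or units transfused, both of which define a major bleed.

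**The case against.** The strongest reply is that the script is not the only route. Section 6.2 tells patients to come in at once for any bleeding and schedules adverse event evaluation at days 7, 14, 30, 60 and 90. Serious events are collected from consent. The case report form questions are unconditional, its header lists days 30 and 60, and a blinded committee adjudicates all bleeding episodes. All of this stands, and it is why the point is about risk of loss. It does not remove the risk: the script is the only questionnaire supplied for the calls, the two adverse event rules cannot both be followed, adjudicators see only what is reported, and recovery at day 90 rests on recall.

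A reader might infer that patients who stopped drug are not asked at all. The script has no skip rule; everyone called hears items 3 and 4, and the wording only invites a wrong no. A reader might also infer that both items exclude injury; only item 4 does. Nor do the adverse event rules conflict with the endpoint definition; they conflict with each other.

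Finally, the case report form mismatch might be read as losing events. It does not: the consequence boxes follow a bleed already recorded as yes. The mismatch affects classification, and the extra boxes could over-classify as easily as under-classify.

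**Conclusion.** The mismatch is established from the text: the scripted bleeding questions are narrower than the outcome analysed, at the only scheduled contacts in a 76-day stretch. Capture may therefore be incomplete and may differ by arm. The contradiction between Sections 8.1 and 8.2 is also plain.

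It would go too far to say that bleeding is under-collected or that apixaban will look safer than it is. The documents give no capture rate and no planning rate for bleeding, unconditional routes exist, and the two likely biases pull in opposite directions. The only arm contrast the plan supports is 12.5 against 2.0 patients expected to have a clot, and the bleeds at issue among them number about 0.5 to 1.25 on placebo at assumed rates of 4% to 10%. No sample size figure changes.

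**What to change.** - **Script.** Reword items 3 and 4 to ask about any bleeding since the last contact, from any cause and whether or not study drug was being taken. Follow a yes with questions that match 3.3: site, medical intervention, admission or higher level of care, evaluation, hemoglobin fall and units transfused.
- **Sections 8.1 and 8.2.** Reconcile them so that bleeding and clot symptoms are asked about specifically at every contact, and state one method of questioning for all other adverse events.
- **Appendix B2.** Align the bleeding items with 3.3. Add admission or higher level of care, evaluation, hemoglobin fall and units transfused. If unscheduled contact and drug interruption are kept, mark them as descriptive and not as classifying criteria.

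The cost is changes of wording to the script, the form and two protocol sections. The calls are already scheduled, and no visit, sample size or clinical rule changes. Label: free improvement.
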